#### RISKS AND HOW MINIMIZED

##### HIV risk counseling

Participants that are tested for HIV to ensure eligibility will undergo HIV risk reduction counseling (e.g. increasing condom use, reducing number of partners, addressing substance abuse, etc.) by the study PI or study staff with provision of condoms and lubricant available freely at the Hope Clinic. HIV rapid testing will then be conducted with a CLIA waived product with finger-stick or whole blood from phlebotomy, depending on the test. Any participant who is found to be HIV positive on rapid testing will be referred for confirmatory testing to their local health department, community based organization that provides HIV testing, or provider of their choice. We will also assist any HIV positive participant in accessing healthcare for HIV infection as needed.

Participants will also be educated about HIV pre-exposure prophylaxis during the study by the coordinator and/or study clinician. After completion of the study, all men who are interested in PrEP for HIV prevention will be linked to community services. A detailed listing of PrEP services available for insured and uninsured clients in Atlanta can be found at [www.preplocator.org](http://www.preplocator.org). [name] is active in PrEP implementation in the Atlanta community and can facilitate these linkages.

### Blood sample collection

The most common risks of blood sample collection are pain at the puncture site, bruising, and a feeling of lightheadedness. To minimize these risks, blood draws will be performed by trained personnel, and will be performed in a secure environment with access to first aid equipment, bandages, and trained healthcare professionals.

### Risk of Genvoya®

Genvoya® is a combination anti-HIV medication that contains the drugs tenofovir alafenamide, emtricitabine, elvitegravir, and cobicistat. Based on clinical trials previously conducted of Genvoya®, the drug showed to be well tolerated (see package insert). According to participants, the most common side effect shown was nausea with diarrhea being the second most common side effect. Of those who reported this adverse event, 0.9% and 1.5 % discontinued treatment regardless of the severity (see package insert). Adverse events associated with Genvoya® can include a transient decrease in renal function and slight decreases in bone mineral density. There is also a possibility of lactic acidosis, which can be hard to identify during early stages. These effects occur with prolonged use of the medication and are not expected to occur with the limited 2-day dosing in this protocol.

Genvoya® can also cause flare-ups in those who have hepatitis B virus. It can cause the Hepatitis B virus to suddenly return in a worse form than before if treatment was provided (see package insert). For this reason, it is important that participants not participate in the study if they are known to have Hepatitis B. Nonetheless, the maximum 2 day dosing regimen for this study is unlikely to cause flare-ups in Hepatitis B even if not diagnosed.

Acquisition of HIV drug resistance is a theoretic concern for HIV positive people taking intermittent dosing of anti-HIV medication. For this protocol, we will test men for HIV at study entry and monitor clinically for high-risk behavior or any signs of acute HIV infection at study visits. If high risk behavior (e.g. unprotected anal intercourse with a man of unknown HIV status) or symptoms of acute HIV infection are reported, and HIV antibody test will be repeated and the participant will be counseled about the need for any follow-up testing. Clinical signs and symptoms of acute HIV infection that will be queried include: fever, fatigue, malaise, skin rash, swollen glands, oral/genital ulcers, myalgia/arthritis(3). [name] will review all reports of clinical signs/symptoms to determine appropriate follow-up and linkage to care as necessary. If a diagnosis of acute HIV infection is thought to be possible or determined by repeat HIV testing, the participant will be discontinued from the study. For this protocol, we will test men for HIV at study entry and monitor clinically for high-risk behavior or any signs of acute HIV infection at study visits.

TITLE OF PROJECT: On-Demand PEP

Emory IRB

PRINCIPAL INVESTIGATOR: [name], MPH

Men will be asked to abstain from receptive anal intercourse for three days prior to drug dosing and during the study protocol in order to limit additional exposures (e.g. semen, douching, additional lubricants) to the rectal mucosa. Men taking Genvoya® will be counseled that they should not expect to achieve protection from HIV infection by taking drug during this study, as they will be provided a limited supply. All men included in the study that have an interest in taking PrEP for HIV prevention, will be referred to an area PrEP provider at the termination of the study. The Hope Clinic has compiled a resource sheet of area providers that will be distributed to interested participants.

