### INCLUSION CRITERIA FOR MSM

- 1) HIV-negative man who reports receptive anal sex with another man in the last 6 months
- 2) Aged 18-49 years
- 3) Not currently taking PrEP and no plans to initiate during study
- 4) Not currently taking PEP
- 5) Able to provide informed consent in English
- 6) No plans for relocation in the next 3 months
- 7) Willing to undergo peripheral blood, penile swabs, urine, and rectal biopsy sampling
- 8) Willing to use study products as directed
- 9) Willing to abstain from receptive anal intercourse 3 days prior to starting study product and for the duration of the study and for 7 days after any rectal biopsy procedure.
- 10) Hepatitis B surface antigen (HBsAg) must be negative (screening lab test)
- 11) Creatine clearance >60 ml/min

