**Group A.1 (n=8; enrollment will close once 4 men complete their biopsy visit):**

**Visit 1(screening):** Eligible MSM will provide written informed consent, be questioned about their medical history, undergo a physical exam (conducted by a study clinician) a rapid HIV test, and a peripheral blood sample for a complete blood count, creatinine, coagulation test, and hepatitis B. Participants will then be asked to return within 1- 6 weeks for visit 2.

**Visit 2:** Participants will be given a one- day supply of Genvoya®. Staff will provide instructions to participant on when to take dose at home. Participants will be asked to dose **24hrs before visit 3** and will be instructed to photograph or videotape themselves taking dose with the timestamp included with their smartphone. Study staff will instruct participants to bring the photo/video to their next visit to provide proof of dosing. Participants will also have the option to send a text to a specified number with the time and date of dose if their phone device does not have video/photo capabilities.

**Visit 3:** Visit 3 takes place 24hrs after home dose. During this visit, drugs will be dispensed to participants, and they will be instructed to take one dose of Genvoya®. Men will be dosed on-site (time of dose will be recorded) and asked to return in 2hrs. Procedures should be done as close to 2hrs as possible with a +/- 1 hour window.

**Visit 4:** Visit 4 takes place 2hrs (+/- 1 hour) after on-site dose. Approximately 24 mL of blood will be drawn, an oral cheek swab, 1 pre- wet penile swabs and 1 dry penile swab, and a urethral swab will be collected. After previous swab collections are complete, participants will be asked to provide a urine sample, some of which will be used for gonorrhea and chlamydia testing, then the practitioner (Principal investigator or Co- investigator) will collect rectal secretion samples by using two swabs and insert an

aptima swab for rectal gonorrhea and chlamydia testing, before the participant undergoes a rectal biopsy via rigid sigmoidoscopy.

Participants will be asked to provide an optional single semen sample, which will be collected at home, no more than 2hrs before/after to biopsy visit.

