All participants who will undergo a rectal biopsy will be informed not to place anything into the rectum and abstain from intercourse 7 days after their rectal biopsy procedure to allow the mucosa to heal. If tested positive for gonorrhea and/or chlamydia, participant will be notified and referred to linkage for treatment.

*Biologic specimens:*

TITLE OF PROJECT: On-Demand PEP  
Emory IRB  
PRINCIPAL INVESTIGATOR: [name], MPH

Biologic specimens collected after the screening visit will be transferred directly to CDC for measurement of study drug levels. Specimens will be labeled with a unique ID that only the Emory study team will be able to link to identifiable information. CDC personnel will not have access to identifiable information.

*Contingency visit:*

Attempts to ensure adherence to the study visits will be made with telephone and/or email reminders to the participant. However, if for example, screening laboratory results are lost or are inconclusive or if a participant has been unable to adhere to study protocol, he may be rescheduled for a future date where the above visit procedures will be performed. These additional visits will be scheduled within the above visit windows.

*Timing of procedures after dose:*

The procedures conducted after dose, particularly those less than 24 hours after dose, should occur as close to the scheduled time points as possible. Protocol deviations will be filed for visits that occur outside of the target windows identified above only if the visit is conducted more than 3 hours beyond the target window defined above for each arm and visit.

*Phone calls/retention contacts:*

While on study, periodic phone calls, texts, or email reminders will occur between study staff and participants to ensure proper retention and adherence to study protocol.

Rectal biopsy procedures

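### After a reported high-risk exposure without symptoms, the protocol directly triggers only a repeat HIV antibody test and counselling, and no remaining dose has to wait for the result

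*Combined protocol and SAP*

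**What the plan says.** Under Risk of Genvoya®, the protocol describes resistance as a theoretic concern for HIV-positive people on intermittent dosing. It therefore tests at study entry and monitors at visits for high-risk behaviour and signs of acute infection. Either kind of report triggers the same response: an "HIV antibody test will be repeated and the participant will be counseled about the need for any follow-up testing". The stated review is narrower than the trigger: the named clinician "will review all reports of clinical signs/symptoms to determine appropriate follow-up and linkage to care as necessary". A stopping rule follows: "If a diagnosis of acute HIV infection is thought to be possible or determined by repeat HIV testing, the participant will be discontinued".

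The entry test is described under HIV risk counseling: "HIV rapid testing will then be conducted with a CLIA waived product", using finger-stick or whole blood. That section also requires referral for confirmatory testing after a positive rapid test. No HIV antigen or RNA test is named anywhere in the document.

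On timing, after the screening visit "Participants will then be asked to return within 1- 6 weeks for visit 2". Under Study visits, a man may join a further arm at least 6 weeks after finishing one. He then starts at visit 2 without repeating visit 1, where the rapid HIV test sits. The inclusion criteria require that he be "Willing to abstain from receptive anal intercourse 3 days prior to starting study product and for the duration of the study".

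**The concern.** The rule exists to catch acute infection before drug is given to a man who has it. Antibody takes time to develop, so a negative antibody result soon after an exposure is weak reassurance. The protocol's own wording allows for this, because it lists infection thought possible separately from infection shown by repeat testing.

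The man the rule fits least well is the one who reports an exposure and feels well. He meets the trigger, but the stated review does not mention him. The dosing text for visits 2 and 3 attaches no condition about an HIV result. He can be dosed, in full compliance with the protocol, on a negative or pending antibody test. At stake is antiretroviral exposure, in a healthy volunteer who gains no direct benefit, during an infection the plan set out to look for.

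**Working it through.** The plan gives no figure for this risk, so the check is mainly textual, with simple counts of days, doses and places.

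**1. What each report leads to (Risk of Genvoya®; visit 2 and 3 text in all dosed arms).**

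| Report | Repeat test and counselling | Stated investigator review | Dose held for result | Discontinuation |
|---|---|---|---|---|
| Symptoms of acute infection | Yes, antibody | Yes | Not stated | Required if infection is thought possible or shown by test |
| Exposure, no symptoms | Yes, antibody | Not stated | Not stated | Same rule, but no criteria for exposure alone |

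**2. Doses still avoidable.** One home dose is handed out at visit 2 and one is taken on site at visit 3. A man who triggers the rule can be spared 2 of 2 doses at visit 2, 1 of 2 at visit 3, and none at visits 4–5. The pre-drug arm receives no drug.

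**3. Age of the entry test at visit 2.**
- First arm: 1–6 weeks = 7–42 days.
- Re-entry: at least 7 days to the first visit 2, plus at least 6 weeks (42 days) after finishing that arm: 7 + 42 = 49 days or more, with no upper limit stated for this interval.

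**4. What abstention covers.** If it starts 3 days before study product, the days between entry test and first dose left uncovered in a first arm are at least 7 − 3 = 4 to 42 − 3 = 39. If the study's duration is taken to start at screening, receptive intercourse is covered throughout, though the separate 3-day term then adds nothing. On either reading the inclusion criterion is limited to receptive intercourse, whereas the example given for the trigger is unprotected anal intercourse of any kind.

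**5. Whether a man held at visit 3 can restart.** Let g be the day of visit 2, counted from screening. Visit 3 is at the earliest day g + 1. If the 6-week interval is applied, the new visit 2 is day g + 1 + 42 = g + 43, the new on-site dose is day g + 44, and the latest sample (96 hours, Arm C) is day g + 48. The Abstract limits time on study to 12 weeks = 84 days.
- g = 7: day 55, within the limit.
- g = 36: day 84, just within it.
- g = 42: day 90, beyond it.

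A restart therefore fits for every screening gap up to 36 days, even in the longest schedule. It brings his total to 1 + 2 = 3 doses. Men are already allowed two doses in each of several arms.

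**6. Room for a lost participant.** Each dosed group has 8 places, and "enrollment will close once 4 men complete their biopsy visit", leaving 4 spare. Over the 7 dosed groups: 56 enrolled, 28 completing, 28 spare. Adding the pre-drug arm (6 enrolled, 3 completing) gives 62 and 31, which matches Study Population. That section expects dropout to use these same places.

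Neither the number of men who will trigger the rule nor the share of infections an antibody test would miss can be derived from the document.

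**The case against.** The strongest reply is that the protocol already has a mandatory stop. A reader might infer that testing and counselling are the only obligations after an exposure report. The document does not support that: discontinuation is required if acute infection is thought possible, and that limb needs no test result. This stands, and it narrows the point. It does not remove it, because the rule names no decision-maker and is not tied to exposure without symptoms.

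Second, a repeat of the entry test would naturally be a rapid test read at the visit, so the result may be known before dosing in practice. That is plausible. It makes the missing hold less serious, but the text neither says the repeat is rapid nor puts the reading before the dose. A laboratory test could itself create the wait.

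Third, the limits of an antibody test are not documented in the protocol, and any test can be negative in the first days after exposure. Both are fair. A better test reduces reliance on judgement without replacing it, so the existing stop must stay.

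Fourth, the adverse-event section runs the study period from enrolment. If enrolment means consent at visit 1, receptive exposure before dosing is already ruled out by instruction. That reading is open, but the monitoring rule exists for men who depart from the instruction, and the inclusion criterion does not cover insertive exposure.

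A reader might also infer that a man held at visit 3 must be replaced. The timeline above does not support a fixed rule.

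**Conclusion.** The gap is real and should be closed, at modest severity. For a reported exposure without symptoms, the steps triggered directly do not match the stated aim of detecting acute infection. Up to two doses at visit 2, or one at visit 3, can be given without a suitable test, a stated review or a known result. The entry test is then 7–42 days old in a first arm and at least 49 days old on re-entry.

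This rests on one assumption from outside the document, that an antibody test may not yet be positive in early infection. No window-period figure is used. The benefit is limited to the few men who report an exposure. The protocol treats resistance as theoretic, exposure is two doses per arm, and men who report nothing gain nothing. No population percentage can be given.

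**What to change.** Amend Risk of Genvoya® as follows.

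1. Replace the HIV antibody test with an HIV antigen/antibody or HIV RNA test.
2. Extend the investigator review to reports of high-risk behaviour, and apply the existing stop for infection thought possible to those reports. State that a negative antibody result alone does not exclude acute infection.
3. At visits 2 and 3, give or dispense no remaining dose until the result has been read and reviewed. Reschedule under Contingency visit where the windows allow, since "These additional visits will be scheduled within the above visit windows". Otherwise leave restart or replacement to the investigator.

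Sampling at visits 4–5 stays as planned.

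The cost falls only on men who trigger the rule: one test, possibly one tube, and possibly a $20 contingency visit. In the dosed arms visits 2 and 3 list no blood draw, and specimens taken after screening go to CDC for drug levels, so any tube needs a clinical laboratory. At visit 3 the dose is due 24 hours after the home dose, so a result not available that day may cost the participant. Each loss uses one of 4 spare places in his group, which is tolerable if it stays occasional.

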#### Rigid sigmoidoscopy and biopsies

Risks associated with lower gastrointestinal endoscopy include colitis from chemicals for endoscope sterilization, bowel perforation, bleeding, diverticulitis, and infection. All biopsies will be completed by either the PI or a delegated, licensed medical professional whom the PI has trained in the procedure. Non-physician medical providers have performed endoscopic procedures for diagnostic and therapeutic procedures for years. Many of these require mastery of flexible sigmoidoscopes, detailed anatomy of the full colon, and familiarity with sedation procedures.(4, 5) Procedures utilizing flexible instruments that access a deeper area of the colon and may or may not require sedation are more complicated and risky than the procedure detailed in this protocol which utilizes a rigid sigmoidoscope and only accesses the sigmoid colon a maximum of 15 cm from the anal verge. Therefore, it is appropriate for a trained, licensed mid-level provider to perform the procedure. [name] team has performed >300 similar procedures for other IRB approved protocols with zero complications.

All procedures will utilize disposable rigid sigmoidoscopes, forceps, and guides to reduce risk of infection and obviate the need for instrument sterilization between participants. To minimize risks, rigid proctoscopy, rather than flexible sigmoidoscopy or full colonoscopy, will be used in this study and the number of biopsies taken will be limited to 10. Colonoscopy has been shown to be associated with a still low, but significantly greater risk of complications than rectosigmoidoscopy.(6) The frequency of serious complications after flexible sigmoidoscopy is extremely low and complications from rigid sigmoidoscopy are presumably even lower, but unknown. In two large studies including a combined 144,832 clinically indicated procedures, the incidence of serious complications ranged from 0.06 to 0.8% utilizing flexible sigmoidoscopy.(6, 7) Obtaining biopsies may be associated with an increased risk of complications. The best available data on the risk of multiple biopsies comes from studies of dysplasia surveillance among patients with long-standing inflammatory bowel disease, in whom large numbers of "blind" biopsies are obtained throughout the colon for early detection of malignant transformation. In two such studies including a combined 3,011 procedures and a median of eight and 17 biopsies, respectively, there was only one serious complication, for an incidence of approximately 0.33%.(8, 9) In a study of subjects undergoing endoscopic procedures exclusively for research purposes, including 64 flexible sigmoidoscopies with a mean of 25 biopsies obtained from the rectosigmoid,

TITLE OF PROJECT: On-Demand PEP  
Emory IRB  
PRINCIPAL INVESTIGATOR: [name], MPH

there were no major complications. Thirteen subjects experienced minor symptoms (self-limited bleeding and pain), which were not related to the number of biopsies.(10)

Most relevant to the current study, a summary of procedures across several Microbicide Trial Network (an NIH-funded, international network designed to develop topical agents for HIV prevention) was published in 2017.(11) This manuscript reported on the safety of 1,004 sigmoidoscopy procedures with >15,000 biopsy collection from 278 research participants. Many participants underwent multiple procedures (median 3 procedures). There were no serious adverse events, and an AE related to sigmoidoscopy was reported in 1.6% of procedures. Eight of the 16 related AEs reported were abdominal pain, flatulence, bleeding, diarrhea, and bloating. Fourteen of the 16 related AEs were grade 1 and 2/16 were grade 2; median time to resolution was 1 day. The authors concluded that repeated intestinal mucosal biopsies for research purposes are safe. Thus, based on the available data, the risk of serious complications from the proposed study procedures, even with up to 10 biopsy specimens, is expected to be very low (<1:5000).

There is theoretical risk of increased acquisition of HIV or other infection if a study participant is exposed soon after the rectal biopsy procedure (i.e. while the mucosal surface is damaged). Therefore, study subjects will be counseled not to engage in anal intercourse for 1 week after the rectal biopsy procedure.

Biologic samples will be coded with a unique identifier prior to processing and storage for immunologic assays. Therefore, lab personnel will be unable to link specimens with participants. Only the PI and designated co-investigators/study personnel will be able to access information to identify specimens of individual participants.

#### BREACH OF CONFIDENTIALITY

All measures will be taken to ensure information provided by participants is kept confidential. Identifying paper information will be kept in a separate locked office and only accessible by the PI and study coordinator. Electronic data will be stored on the Redcap server or the Emory School of Medicine HIPAA compliant servers, which will be accessible to the PI and study coordinator only. All study specimens will be labeled with a unique identifier prior to transport to CDC. Identifying information will not be shared with laboratory collaborators at the CDC and they will be unable to link the study ID to any identifying information. Any demographic data shared with CDC will also be stripped of HIPAA identifiers prior to sharing.

